## **ADEQUACY OF PROTECTION AGAINST RISKS**

### **Recruitment and Informed Consent**

Participants will be recruited through the lung cancer screening programs at Hollings Cancer Center and Yale Cancer Center/Smilow Cancer Hospital at Yale-New Haven and the Ralph H. Johnson Veteran Administration. Informed consent will be obtained prior to beginning the study.

**Protection Against Risk.** We will take the following steps to reduce the direct risk of participating in the study:

(a) If offended in any way, participants can terminate any part of participation without penalty. In all of the preliminary experiments reported in this proposal, no participant reported being unduly distressed or upset about his or her participation, although occasionally participants do drop out because they are no longer interested in the study or because it is taking too long and they have other obligations. To date, no one has expressed significant regret about having participated.

(b) If a participant or potential participant appears extremely distraught or clearly preoccupied, investigators will use their discretion as to whether or not to attempt to enroll the individual into the study or suggest that their participation stop.

(c) If a participant reports an adverse effect of the NRT, we will work with them to ensure that they are using the medication properly. If it is determined that they have been using the medication properly and are still experiencing an adverse effect, they will be encouraged to discontinue use of the NRT.

(d) Several steps will be taken to safeguard the confidentiality of subjects and their data. All research data that is collected will be assigned a study participant number and that number will only identify participants in digital databases. The names of participants will not be associated with this data and assessments will be maintained

according to participant study number. A master list connecting participant study numbers to participant names will be kept online on the Box MUSC approved encrypted website where only senior level project staff will have access to the information. Any information published as a result of the study will be such that it will not permit identification of any participant. For VA patients, their consent forms will be stored in a locked cabinet in [name] space on VA premises and their MUSC consent and HIPAA will be stored in a locked cabinet on MUSC premises.

Medical records are maintained under the person's name, but the study number is not entered anywhere into that record. Right to privacy for participation in this research will be protected through coding of data and proper storage of research records. The Principal Investigator will maintain a list of IDs and the corresponding names online on the BOX MUSC approved encrypted website. Consistent with mandated reporting requirements for health providers, we advise participants that in the case of child abuse or neglect, threat of injury to self or others, or intention to destroy property, that we may need to intervene and report that information to the proper authorities. Subjects will be informed of this limit to confidentiality as it is stated in the informed consent document. For VA patients, there will be a note entered in the CPRS system that they have been consented to participate in an MUSC study but no other notations of study procedures will appear in their medical records. The data will be stored in a locked room for 7 years after the final data is collected. The PI and the research staff will have access to PHI. Organizations that have a responsibility for protecting human participants, including the MUSC IRB, may have access to subjects' medical records containing PHI. Additionally, the funding agency (National Cancer Institute) may have access to subjects' medical records containing PHI.

#### **POTENTIAL BENEFITS OF THE PROPOSED RESEARCH TO THE SUBJECTS AND OTHERS**

Participants will receive advice about quitting smoking. Subjects participating in this study may benefit from the information provided to them the counselor by having their motivation to quit smoking bolstered and by receiving advice that helps them to quit smoking. Although the investigators cannot know for sure whether this study will be of any direct benefit to participants, the results of the study will facilitate the development of more effective smoking cessation intervention materials, which will promote tobacco and cancer control.

#### **IMPORTANCE OF THE KNOWLEDGE TO BE GAINED**

Although the proposed research poses minimal risks to participants, it has high potential for advancing knowledge in the field of smoking cessation. The proposed research will augment current knowledge on the efficacy of interventions administered in the context of lung cancer screening. Administering a sample of NRT and gain-framed messages may help to identify a low-cost method for increasing the effectiveness of a moderate-intensity intervention for smoking cessation that has the potential to reach smokers at high risk of lung cancer, thereby bolstering tobacco and cancer control efforts across the United States. Given the minimal risks in the study and the potentially great benefit to science, the risk/benefit ratio in this study appears quite favorable.

#### **DATA AND SAFETY MONITORING PLAN**

Monitoring for data integrity and safety will be the responsibility of the investigators, the MUSC Institutional Review Board, and the Yale University Human Investigation Committee.

**Data Monitoring.** For this review process, we evaluate a semiannual report of aggregate data that contains screening data, baseline demographics, retention data, adverse events data, accrual status including projections, times to milestones, and any other data that will help in the assessment of the experiments. Based on this report, we will decide whether we will: 1) continue recruitment unchanged; 2) continue with a protocol amendment; 3) stop the study pending further investigation. If after assessment, we feel that a protocol amendment is needed, the MUSC IRB and the Yale HIC will be immediately informed by the site PIs.

**Safety Monitoring.** This protocol presents minimal risks to participants. The study involves receiving gain-framed messages and/or a 2-week sample of NRT, and to complete follow-up interviews. The only risk that can be anticipated from this study is loss of confidentiality, and this will be protected using the procedures described

in the "Sources of Materials" section above. Nonetheless, because we anticipate that behavior change (which will pose minimal risk to participants) will be a product of participating, we have developed a safety monitoring plan to report adverse events resulting from behavioral changes.

**Monitoring to identify adverse events.** Prior to implementing the randomized study, research staff will be trained to identify adverse events. Research staff will be instructed to provide the Project Coordinator a detailed description of the event. The Project Coordinator will grade the event in conjunction with the PI within 24 hours. The following additional individuals will be informed immediately of serious adverse events: (a) all Co-investigators; (b) the National Cancer Institute; (c) the MUSC Institutional Review Board; and (d) the Yale University Human Investigation Committee. All of these individuals and committees will receive a copy of an SAE Form within 48 hours.

**Plan for grading adverse events.** Serious Adverse Events (SAE). The FDA's definition of serious adverse events (21 CFR 312) will be used. Serious Adverse Events include any untoward medical occurrence that at any dose results in death or the immediate risk of death, hospitalization or the prolonging of an existing hospitalization, persistent or significant disability/incapacity or a congenital anomaly/birth defect, new cancer, or medication overdose. Adverse events will be defined and graded for risk as follows:

Coding of Severity:

- 0 = No adverse event or within normal limits
- 1 = Mild adverse event
- 2 = Moderate adverse event
- 3 = Severe, resulting in psychiatric or medical hospitalization
- 4 = Life-threatening adverse event
- 5 = Fatal adverse event

Coding of Attribution will be made for adverse events grade 3 and above (ie, serious adverse events):

- 1 = Unrelated to study interventions
- 2 = Unlikely relationship to study interventions
- 3 = Possible relationship to study interventions
- 4 = Probable relationship to study interventions
- 5 = Definite relationship to study interventions

**Plans for reporting serious unanticipated and anticipated adverse events.** Serious adverse events, whether unanticipated or anticipated, will be reported immediately (within 24 hours) to the MUSC Institutional Review Board, the Yale University Human Investigation Committee, and to the National Cancer Institute, and a written report will be submitted within 48 hours. The PI will evaluate the adverse event and determine whether the adverse event affects the Risk/Benefit ratio of the study and whether modifications to the protocol or the consent procedures are required.

**Plans for reviewing and reporting nonserious anticipated or unanticipated adverse events.** Any participants' experiences of anticipated and unanticipated adverse events will be reported on an annual basis to the MUSC Institutional Review Board, the Yale University Human Investigation Committee, and the National Cancer Institute as part of an annual progress report (NCI) and annual re-approval (MUSC Institutional Review Board and the Yale University Human Investigation Committee).

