**NRT sampling:** Participants in the medication arm (GM+M) will be given a 2-week long supply of both nicotine patch and lozenge. NRT samples will be delivered in addition to all standard care treatment described above. Given the very brief 'intervention' time (few minutes), we believe that treatment groups will be essentially time-matched. We will provide a 2-week supply of both 4 mg lozenge and 21mg nicotine patches provided in the original packaging. Detailed information on each product, including instructions for use, will be provided in the take-home packet, which will include FAQs and related information intended to dispel medication misperceptions. Patients who are receiving nicotine patches and lozenges will be given the option to try these over-the-counter products (i.e., a patch and a lozenge) at the time of their study visit with aid from the research staff and will receive handouts and instructions about proper use of the NRT. We provide both patch and lozenge for four reasons. **First**, a number of studies demonstrate their efficacy when used singularly. **Second**, they are both over the counter, increasing their utility in various populations, particularly within lung cancer screening settings where eligibility is minimal and instructions on use require nominal discussion. **Third**, whereas the patch provides a steady dose of nicotine throughout the day, the lozenge is used ad libitum and provides acute nicotine administration. These two mechanisms might appeal to smokers differently. **Fourth**, two studies have shown that combined use of patch + lozenge is superior over placebo and single NRT products. We neither explicitly advise nor discourage combined use. Thus, this is an opportunity for smokers to learn about two NRT products, to be used individually or together (participant choice, including none at all). We will caution all participants on signs of receiving too much nicotine (nausea, dizziness), and will monitor adverse events, expected to be rare/mild. Given our inclusive study criteria, some study participants who have low nicotine dependence will receive the starter package of NRT. However, given recent evidence that dual NRT benefits most low dependence smokers, we feel this is appropriate. We do not offer a placebo comparison because we are interested in the provision of medication vs. not (and not to determine if effects are pharmacologic). However, participants not receiving the starter kit of NRT will still be advised to use evidence based medications, including NRT, per standard guidelines. The NRT for MUSC patients will be stored in a cabinet in the Tobacco Treatment Program offices. The door to the office suite locks. The NRT for VA patients will be obtained via the research pharmacy at the Ralph H Johnson VA Medical Center.

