Research data will be collected using in-person interviews and self-reports. All identifiable information will be stored in a locked file cabinet. All identifiable information collected from VA patients will be stored in a locked cabinet in [name] office room C405 at the Ralph H Johnson VA Hospital. All participants will be assigned a study participant ID made up of numbers and letters. Subsequently, participants will be identified in the Case Report Forms (CRFs) only by that number (e.g., CM24). A list of MUSC IDs and the corresponding names will be maintained by the Principal Investigator and stored on the MUSC BOX.Com site. Digital data with PHI will be stored on a secured server. A list of VA IDs and the corresponding names will be maintained by the site Principal Investigator, [name], and stored on the V drive behind the VA firewall. Digital data without PHI may be stored and analyzed on a laptop or desktop computer.

**Potential Risks.** The risks to participating in these studies are minimal. Participants are informed in advance about the content of the educational materials that they will receive and the kinds of questions that they will be asked. They are also informed that they may terminate participation without penalty. Moreover, they are informed that, if any pre- or post-intervention question seems too personal or if they prefer not to respond for any reason, they can skip the question without penalty. There is also the risk of loss of confidentiality and privacy. Some participants will be offered nicotine replacement therapy (NRT), and there are risks in taking NRT. The NRT used in this study (patch and lozenge) is a standard smoking cessation intervention and is available over-the-counter. The most common adverse effect of nicotine transdermal delivery is topical skin irritation, ranging from mild erythema to a more generalized skin reaction, frequently in subjects with a history of eczematous dermatitis. The most common adverse effects of nicotine replacement lozenges are upset stomach and heartburn.

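### Severity grade 3 requires hospitalization and is equated with seriousness, so a severe reaction managed without admission, or an SAE without admission, has no clear grade and may get no attribution code

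*Combined protocol and SAP*

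**What the plan says.** Under Plan for grading adverse events, severity runs from 0 to 5. Mild and moderate carry no criteria; the moderate entry is simply "2 = Moderate adverse event". The next step is "3 = Severe, resulting in psychiatric or medical hospitalization", followed by "4 = Life-threatening adverse event" and then fatal. Only step 3 refers to place of care.

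The attribution rule comes straight after: "Coding of Attribution will be made for adverse events grade 3 and above (ie, serious adverse events"). The SAE definition in the same section covers death and immediate risk of death, and then "hospitalization or the prolonging of an existing hospitalization, persistent or significant disability/incapacity or a congenital anomaly/birth defect, new cancer, or medication overdose". Admission is therefore one route to seriousness among several.

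On expected reactions, Potential Risks describes patch skin irritation "ranging from mild erythema to a more generalized skin reaction", and names upset stomach and heartburn for the lozenge. The NRT sampling paragraph mentions nausea and dizziness as signs of too much nicotine and says staff "will monitor adverse events, expected to be rare/mild". Only the GM+M arm is given NRT by the study.

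**The concern.** Severity describes how intense an event is. Seriousness describes its outcome or what it led to. Step 3 merges the two by making admission part of the label, and the attribution rule then states the merger outright. Two kinds of event do not fit: intense reactions treated outside hospital, and events that are serious for a reason other than admission.

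Both kinds are foreseeable here. The expected NRT reactions vary in intensity and would usually be managed without admission (an assumption; the documents give no rates). A new cancer diagnosed without admission is plausible among people having lung screening. At stake is whether the safety record can show how severe such events were and whether they were judged related to the study intervention. Because attribution starts at grade 3, the relatedness judgement can be lost along with the severity label.

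**Working it through.** The plan states no figure to reproduce and no arithmetic applies. The check takes the scale, the attribution rule and the SAE definition from Plan for grading adverse events and applies them literally to five kinds of event.

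1. **Severe, admitted.** Grade 3, SAE, attribution coded. The three rules agree.
2. **Life-threatening, treated outside hospital.** Grade 4 has no admission condition. The event is also an SAE through immediate risk of death, and attribution is coded. The rules agree.
3. **Severe, not life-threatening, not admitted, no SAE criterion met.** Grade 3 fails on its hospitalization condition, and grades 4 and 5 do not apply. The highest code left is 2. Attribution is not coded, because it covers only "adverse events grade 3 and above (ie, serious adverse events"). As a non-serious event it is reported annually.
4. **New cancer, overdose or lasting disability, not admitted and not life-threatening.** This is an SAE by definition, so expedited reporting applies. On the scale it cannot meet grade 3, so the grade threshold says no attribution, while the parenthetical says SAEs are attributed. The rules conflict.
5. **Admitted for an event of moderate intensity.** This is an SAE through hospitalization. The word severe points away from grade 3, but the admission and the parenthetical equation point to it. On that equation it is coded 3 and attributed, although it was not severe.

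So cases 1 and 2 code cleanly, case 3 loses severity and attribution, case 4 is contradictory, and case 5 is graded by setting rather than intensity. No other section supplied gives a second severity scale or a rule that resolves cases 3 to 5.

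Next, what the grade feeds. The adverse event paragraph of Statistical Analysis compares AE and SAE frequencies and specifies no analysis by grade. The semiannual report under Data Monitoring includes adverse event data in aggregate, with no stated breakdown by grade or arm. The grade's one stated consequence is therefore to trigger attribution.

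Finally, the remedy on the same five cases. Suppose grade 3 is defined by intensity, hospitalization is a separate field, and attribution is coded for every SAE and every grade 3 or above. Then case 3 becomes grade 3 with attribution. Case 4 is graded by intensity and attributed as an SAE. Case 5 becomes grade 2 with hospitalization marked yes, and is attributed as an SAE. Cases 1 and 2 do not change. The last clause is essential: if the parenthetical were deleted while attribution stayed tied to grade alone, case 5 would lose the attribution it has now.

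**The case against.** The strongest reply is that little depends on the grade. A reaction of the third kind counts in the AE frequency whether it is coded 2 or 3. Statistical Analysis gives particular attention to events that lead to suspended treatment or leaving the study, whatever their grade. Protection Against Risk, item (c), encourages stopping NRT when an adverse effect persists despite proper use, so a troublesome reaction may well surface by that route. Staff must give a full description of each event, and non-serious events go each year to both review boards and the funder. An admission criterion is also more objective than intensity in a trial without placebo.

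Most of this stands, and it limits the size of the point. Stopping is a weak marker of severity, though, because the supply lasts two weeks and use is left to the participant. None of these routes restores the missing attribution code.

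A second reply is that the hospitalization phrase is only illustrative. The text does not order anyone to code such events as moderate; that is the result of a literal reading. But the parenthetical equating grade 3 and above with SAEs supports the literal reading, and if graders differ on it, coding will vary between them.

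A reader might infer more: that an excess of severe NRT reactions would be hidden in a reported severity table, or that the scale can show no severe outpatient reaction at all. The documents support neither. No severity table is planned, and grade 4 is open to events treated outside hospital.

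**Conclusion.** The point holds as a coding defect with a modest effect. The severity scale, the attribution rule and the SAE definition cannot all be applied as written, and these passages need to be reconciled. The loss is severity and relatedness information on two kinds of event: severe, non-life-threatening reactions without admission, and SAEs without admission. Since only GM+M receives study NRT, the first kind is likely to fall mainly in that arm.

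The primary result and the specified AE and SAE comparisons are unaffected. The number of events concerned cannot be estimated from the documents, which give no rates of NRT reactions or admissions. The conclusion rests on reading step 3 literally and on the assumption that most expected NRT reactions are managed without admission. The contradiction for SAEs without admission needs no assumption about NRT reactions.

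**What to change.** In Plan for grading adverse events:

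- define grade 3 by intensity, irrespective of admission;
- record hospitalization as a separate yes/no seriousness field;
- delete the parenthetical that equates grade 3 and above with SAEs;
- state that attribution is coded for every SAE and for every event of grade 3 or above.

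Apply this going forward. If events already logged are re-graded from their descriptions, the grader should be masked to arm where possible, because the trial has no placebo and intensity is a judgement. Keep the codes first assigned alongside the new ones.

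Expedited reporting continues to follow the SAE definition and does not change. The cost is a short protocol amendment, one extra field, slightly more coding work, and a few more events shown as severe.
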